### **6.2.9     *Ventilation Use***

The subject's ventilator use will be recorded at the times/dates according to the schedule as shown in Appendix A (Schedule of Procedures).

### **6.2.10    *Phone Assessments***

Monitoring telephone calls will occur on Study Days 8, 43, 57, 71, 106, 127, 134, 148, 189, 197, 218, 239, 274, 295, 316, 358, 380, 400, 421, 463, 484, 506, 526, 547, 589, 610, 632, 652, 673, 715, 736, 758, 778, 799, 841, 862, 884, 904, 925, 967, 988, 1010, 1030, 1051, 1093, 1114, 1136, 1156, 1177, 1219, 1240, 1262, 1282, 1303, and 1324 (i.e., approximately every 3 weeks between study visits). Changes in concomitant medications and adverse events will be recorded. In addition, information on the subject's ventilator use and SMA disease status will be collected.

### **6.2.11    *Safety Evaluations***

Safety will be evaluated by assessment of AEs including SAEs as described in Section 9. Additional safety evaluations include the following parameters:

- Neurological examinations (HINE)

- Vital signs
- Physical examinations and weight
- Clinical laboratory tests (serum chemistry, hematology, urinalysis)
- CSF laboratory tests (cell count, protein, glucose)
- Electrocardiogram (ECG)
- Use of concomitant medications

## 7. STUDY DRUG

### 7.1 Study Drug

There are 2 types of Study Drug that may be provided for this study:

- a. Study Drug at a concentration of 20 mg/mL which is diluted prior to use; this is described as the ‘Two-Vial’ configuration. See Section 7.1.1 for more details.
- b. Study Drug at a concentration of 2.4 mg/mL; this is described as ‘Ready-to-Use Vial’ configuration. See Section 7.1.2 for more details.

#### 7.1.1 *Two-Vial Configuration (ISIS 396443 and Diluent) Description*

ISIS 396443 active drug product and artificial CSF diluent are manufactured by Ionis Pharmaceuticals, Inc., Carlsbad, CA, USA. The active drug product is supplied at a concentration of 20 mg/mL as a 2.5 mL fill volume in a 5 mL clear glass vial. The diluent (artificial CSF) is supplied as a 20 mL fill volume in a 30 mL clear glass vial. These configurations allow for various clinical doses by using different dilution procedures between the active drug product and diluent vials. Study Drug characteristics are described in Table 1. More details are provided in the Investigators Brochure.

**Table 1 Study Drug Characteristics**

Study Drug	ISIS 396443	Diluent (artificial CSF)
Strength	20 mg/mL	NA
Volume/vial	2.5 mL solution per vial	20 mL solution per vial
Route of Administration	IT injection	IT injection

ISIS 396443 and the diluent (artificial CSF) must be stored securely at 2° C to 8° C. ISIS 396443 must be protected from light.

### **7.1.2 Ready-To-Use Vial Configuration Description**

In the 'Ready-to-use' vial configuration, the Study Drug is supplied in 6 mL clear glass vials at a concentration of 2.4 mg/mL. The Study Drug and its storage and preparation instructions will be provided by the Sponsor or designee. Study Drug characteristics are listed under Table 2.

**Table 2 Study Drug Characteristics: Ready-To-Use Vial Configuration**

Study Drug	ISIS 396443 Drug Product
Strength	2.4 mg/mL
Volume/vial	5.0 mL solution per vial
Route of Administration	IT injection

ISIS 396443 must be stored securely at 2° to 8° C and protected from light.

### **7.2 Packaging and Labeling**

Ionis Pharmaceuticals, Inc. will provide the Site Pharmacists with packaged Study Drug labeled in accordance with regulatory requirements.

### **7.3 Study Drug Accountability**

The study staff is required to document receipt, dispensing and return of Study Drug supplies provided by the Sponsor. Drug accountability documentation and all used and unused Study Drug vials (ISIS 396443 and diluent) must be returned to Ionis Pharmaceuticals, Inc. or designee.

## **8. TREATMENT OF SUBJECTS**

### **8.1 Study Drug Administration**

Each subject will receive a single IT bolus (1-3 minute) LP injection of Study Drug using a 'spinal anesthesia' needle and 5 mL syringe. A 22G spinal anesthesia needle is recommended. The target site for needle insertion is the L3/L4 space, but may be 1 segment above or 1-2 segments below this level, if needed. Prior to the injection 5-6 mL of CSF fluid is to be collected for analyses. Depending on institutional guidelines, anesthesia or sedation may be used for the LP procedure, following institutional procedures. Spinal ultrasound may be used for the LP procedure, if deemed necessary, but is not required.

Table 3 outlines the dose equivalent and ISIS 396443 concentration for ISIS 396443 dose cohorts to be delivered during the 'loading' dosing treatment period (i.e., dosing on Days 1, 15 and 85). Study Drug dosing during the 'loading' dosing treatment period will be done using the two-vial configuration.

Table 4 outlines the dose equivalent and ISIS 396443 concentration for ISIS 396443 to be delivered during the 'maintenance' dosing treatment period (i.e., dosing on Days 253, 379, 505, 631, 757, 883, 1009, 1135, and 1261). Study Drug dosing during the 'maintenance' dosing

treatment period will be done using the two-vial configuration and will transition to the ready-to-use vial configuration once the current protocol amendment has been approved.

**Table 3      ISIS 396443 Dose Equivalents and Concentration During the ‘Loading’ Dosing Treatment Period**

Cohort	Dose Equivalent (mg)	Concentration (mg/mL)	Injection Volume (mL)
1	6	1.2	See Table 5
2	12	2.4	See Table 5

**Table 4      ISIS 396443 Dose Equivalent and Concentration During the ‘Maintenance’ Dosing Treatment Period**

Cohorts	Dose Equivalent (mg)	Concentration (mg/mL)	Injection Volume (mL)
1 and 2	12	2.4	See Table 5

The volume of the injection will be adjusted based on the subject’s age. Subjects who are older than 24 months (730 Days) on the day of dosing will receive the full 12 mg dose of the Study Drug (5 mL). For subjects younger than 24 months of age, the volume of the injection will be adjusted based on the subject’s age on the day of dosing per Table 5, such that each subject will receive a 12 mg equivalent dose based on CSF volume scaling.

**Table 5      ISIS 396443 Dose Volume to be Injected**

Age	Estimated CSF Volume*	Injection Volume (mL)
0-3 months (0-90 days)	120 mL	4 mL
3-6 months (91-182 days)	130 mL	4.3 mL
6-12 months (183 – 365 days)	135 mL	4.5 mL
12-24 months (366 – 730 days)	140 mL	4.7 mL
> 24 months (> 730 days)	150 mL	5.0 mL

\* Matsuzawa et al. 2001

Please refer to the Study Drug Manual provided by the Sponsor for detailed instructions for Study Drug preparation and administration.

## **8.2 Other Protocol-Required Drugs**

There are no other protocol required drugs, but depending on institutional guidelines anesthesia or sedation may be used for the LP procedure, following institutional procedures.

## **8.3 Other Protocol-Required Procedures**

There are no other protocol-required treatment procedures.

## **8.4 Treatment Precautions**

Subjects will be encouraged to lie flat for 1 hour following dosing, if possible.

## **8.5 Safety Monitoring Rules**

Please refer to the Guidance to Investigator section of the Investigator Brochure.

## **8.6 Stopping Rules**

Please refer to Section 8.8. There are no additional specific stopping rules for this study but the Investigator should discuss significant concerns relating to individual subjects with the Ionis Medical Monitor to ensure that it is appropriate for the subject to continue Study Drug.

## **8.7 Adjustment of Dose and/or Treatment Schedule**

No adjustment of dose is permitted. In the event of a concurrent illness that would prevent the dosing procedure from being performed safely, an adjustment in the dose schedule may be permitted, but must be approved by the Sponsor Medical Monitor. In this case, the scheduled Day 15 dosing visit may be delayed until up to Day 70 and the scheduled Day 85 dosing visit may be delayed up to Day 120. The scheduled dosing visits during the 'maintenance' period (i.e., Days 253, 379, 505, 631, 757, 883, 1009, 1135, and 1261) may be delayed by up to 8 weeks.

## **8.8 Discontinuation of Study Treatment**

A subject must permanently discontinue study treatment for any of the following:

- The subject withdraws consent
- The subject experiences an adverse event that necessitates permanent discontinuation of study treatment
- The subject experiences a DLT as defined in Section 3.7

The reason for discontinuation of study treatment must be recorded in the Case Report Form (CRF) and source documentation.

Subjects that discontinue treatment will enter the post-treatment follow-up period unless consent is withdrawn (see Appendix A).

## **8.9 Withdrawal of Subjects from the Study**

Subjects must be withdrawn from the study for any of the following:

- Withdrawal of consent

- The subject is unwilling or unable to comply with the protocol

Other reasons for withdrawal of subjects from the study might include:

- At the discretion of the Investigator for medical reasons
- At the discretion of the Investigator or Sponsor for noncompliance
- Significant protocol deviation
- Administrative decision by the Investigator or Sponsor

All efforts will be made to complete and report the observations as thoroughly as possible up to the date of withdrawal. All information, including the reason for withdrawal from Study, must be recorded in the CRF.

Any subject who withdraws consent to participate in the study will be removed from further treatment and study observation immediately upon the date of request. These subjects should be encouraged to complete the early termination study procedures and observations at the time of withdrawal (Appendix A).

For subjects withdrawn for reasons other than withdrawal of consent every effort should be made to complete the early termination study procedures and observations at the time of withdrawal (see Appendix A).

## **8.10 Concomitant Therapy and Procedures**

The use of concomitant therapies or procedures defined below must be recorded on the subject's CRF. AEs related to administration of these therapies or procedures must also be documented on the appropriate CRF.

### **8.10.1 Concomitant Therapy**

A concomitant therapy is any non-protocol specified drug or substance (including over-the-counter medications, herbal medications and vitamin supplements) administered between screening and last telephone contact.

Subjects should consult with the Site Investigator or qualified designee prior to initiating any new medication, including non-prescription compounds or any other non-drug therapy.

#### **Allowed Concomitant Therapy**

Throughout the study, Site Investigators or designated licensed physicians involved in the study may prescribe concomitant medications or treatments deemed necessary for adverse events or to provide adequate supportive care.

#### **Disallowed Concomitant Therapy**

Study subjects are prohibited from receiving other experimental agents during the study. This includes marketed agents being used off-label and/or at experimental doses that are being tested

for the treatment of SMA. The following agents are specifically prohibited: valproate, riluzole, carnitine, creatine, sodium phenylbutyrate, hydroxyurea, salbutamol.

### **8.10.2 Concomitant Procedures**

A concomitant procedure is any therapeutic intervention (e.g., surgery/biopsy) or diagnostic assessment (e.g., blood gas measurement, bacterial cultures) performed between screening and last visit.

## **9. SERIOUS AND NON-SERIOUS ADVERSE EVENT REPORTING**

### **9.1 Sponsor Review of Safety Information**

Safety information will be collected, reviewed, and evaluated by the Sponsor in accordance with the Safety Management Plan throughout the conduct of the clinical trial.

### **9.2 Regulatory Requirements**

The Sponsor is responsible for regulatory submissions and reporting to the Investigators of SAEs including suspected unexpected serious adverse reactions (SUSARs) per the International Conference on Harmonization (ICH) guidelines E2A and ICH E6. Country-specific regulatory requirements will be followed in accordance with local country regulations and guidelines.

IRBs/REBs will be notified of any serious adverse event (SAE) according to applicable regulations. The DSMB will be notified of any SAE as specified in the DSMB charter.

The Sponsor will evaluate the available information and decide if there is a reasonable possibility that the Study Drug caused the AE and, therefore, meets the definition of a SUSAR.

For the purpose of regulatory reporting of SUSARs, there are no “expected” AEs in this study population. For Study Drug “expected” AEs, refer to the Investigator Brochure.

### **9.3 Definitions**

#### **9.3.1 Adverse Event**

An adverse event is any unfavorable and unintended sign (including a clinically significant abnormal laboratory finding, for example), symptom, or disease temporally associated with the study or use of investigational drug product, whether or not the AE is considered related to the investigational drug product.

#### **9.3.2 Adverse Reaction and Suspected Adverse Reaction**

An adverse reaction is any adverse event caused by the Study Drug.

A suspected adverse reaction is any adverse event for which there is a reasonable possibility that the drug caused the adverse event. A suspected adverse reaction implies a lesser degree of certainty about causality than an adverse reaction.

#### **9.3.3 Serious Adverse Event (SAE)**

A serious adverse event is any adverse event that in the view of either the Investigator or Sponsor, meets any of the following criteria:

- Results in death
- Is life threatening: that is, poses an immediate risk of death at the time of the event  
An AE or suspected adverse reaction is considered “life-threatening” if, in the view of either the Investigator or Sponsor, its occurrence places the subject at immediate risk of death. It does not include an AE or suspected adverse reaction that, had it occurred in a more severe form, might have caused death.
- Requires inpatient hospitalization or prolongation of existing hospitalization  
Hospitalization is defined as an admission of greater than 24 hours to a medical facility and does not always qualify as an AE
- Results in a persistent or significant incapacity or substantial disruption of the ability to conduct normal life functions
- Results in congenital anomaly or birth defect in the offspring of the subject (whether the subject is male or female)
- Important medical events that may not result in death, are not life-threatening, or do not require hospitalization may also be considered serious when, based upon appropriate medical judgment, they may jeopardize the subject and may require medical or surgical intervention to prevent one of the outcomes listed in this definition. Examples of such medical events include allergic bronchospasm requiring intensive treatment in an emergency room or at home, blood dyscrasias or convulsions that do not result in inpatient hospitalization, or the development of drug dependency or drug abuse.

## **9.4 Monitoring and Recording Adverse Events**

Any pre-existing conditions or signs and/or symptoms present in a subject prior to the start of the study (i.e., before informed consent) should be recorded as Medical History and not recorded as AEs unless the pre-existing condition worsened. The Investigator should always group signs and symptoms into a single term that constitutes a **single unifying diagnosis** if possible.

### **9.4.1 Serious Adverse Events**

In the interest of subject safety, and in order to fulfill regulatory requirements, all SAEs (regardless of their relationship to Study Drug) should be reported to the Sponsor within 24 hours of the Study Center’s first knowledge of the event. The collection of SAEs will begin after the subject signs the informed consent form and stop at the end of the subject’s follow-up period which is defined as the subject’s last visit. When the Investigator is reporting by telephone, it is important to speak to someone in person versus leaving a message. An Initial Serious Adverse Event Form should be completed and a copy should be faxed to the Sponsor.

Detailed information should be actively sought and included on Follow-Up Serious Adverse Event Forms as soon as additional information becomes available. All SAEs will be followed until resolution. SAEs that remain ongoing past the subject’s last protocol-specified follow-up visit will be evaluated by the Investigator and Sponsor. If the Investigator and Sponsor agree the subject’s condition is unlikely to resolve, the Investigator and Sponsor will determine the follow-up requirement.

#### **9.4.2 Non-Serious Adverse Events**

The recording of non-serious AEs will begin after the subject signs the informed consent form and will stop at the end of the subject's follow-up period, which is defined as subject's last visit. The Investigator will monitor each subject closely and record all observed or volunteered AEs on the Adverse Event Case Report Form.

#### **9.4.3 Evaluation of Adverse Events (Serious and Non-Serious)**

The Investigator's opinion of the following should be documented on the Adverse Event Case Report Form:

##### **9.4.3.1 Relationship to the Study Drug**

The event's relationship to the Study Drug is characterized by one of the following:

- **Related:** There is clear evidence that the event is related to the use of Study Drug e.g., confirmation by positive re-challenge test
- **Possible:** The event cannot be explained by the subject's medical condition, concomitant therapy, or other causes, and there is a plausible temporal relationship between the event and Study Drug administration
- **Unlikely/Remote:** An event for which an alternative explanation is more likely (e.g., concomitant medications or ongoing medical conditions) or the temporal relationship to Study Drug administration and/or exposure suggests that a causal relationship is unlikely (For reporting purposes, Unlikely/Remote will be grouped together with Not Related)
- **Not Related:** The event can be readily explained by the subject's underlying medical condition, concomitant therapy, or other causes, and therefore, the Investigator believes no relationship exists between the event and Study Drug

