### **3.7 Dose Limiting Toxicity**

At the onset of the study, a DLT is defined as an adverse event that in the judgment of a Site Investigator is of sufficient significance to be dose limiting, is possibly or definitely related to Study Drug (i.e., the AE is substantially less likely to occur in subjects not treated with Study Drug), and that is not a known: 1) sign or symptom of SMA disease, or 2) effect of the LP injection procedure.

If a suspected DLT occurs during injection of Study Drug, treatment of the subject with Study Drug should be stopped (i.e., the injection should be immediately discontinued). The Site Investigator should contact the Ionis Medical Monitor as soon as possible following any dosing discontinuations to discuss the case. The DSMB will also be informed and will determine if any relevant findings have been observed with other subjects in the study.

Subjects that experience a DLT will discontinue study treatment but will be monitored by follow-up safety visits.

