#### **3.6.1 Adverse Events**

The incidence of AEs will be summarized by Medical Dictionary for Regulatory Activities (MedDRA) preferred term and system organ class for:

- Any treatment emergent adverse events
- Related treatment emergent adverse events. Related adverse event is defined as those events with related or possible related relationship to study drug.
- Any treatment emergent adverse events by severity
- Related treatment emergent adverse events by severity
- Serious treatment emergent adverse events
- Serious and related treatment emergent adverse events.
- Lumber puncture related treatment emergent adverse events. Lumber puncture related adverse event is defined as those events with related or possible related relationship to study procedure/other study drug.

AEs that lead to treatment discontinuation will be listed separately. Early dosing termination and early study termination will be summarized by termination reason.

A treatment emergent adverse event is defined as an event occurring after the initiation of study treatment and before the end of the follow-up period. Non-treatment emergent adverse event will be flagged in the data listing.

If there is no “Formlink” link, and the AE (start date/time) occurs after the subject’s first dosing date/time, then the AE is treatment-emergent. Otherwise, if the AE (start date/time) occurs prior to the subject’s first dosing date/time, then the AE is not treatment-emergent.

If there is a “Formlink” link between two AE records, then we compare them pairwise, and consider two cases, where we compare the AE severity (mild/moderate/severe) between the two records in the pair. We chronologically order the 2 records (by AE start date) and refer to the “first” and “second” AEs.

Case 1: The first AE record in the pair occurs before first dosing, and the second record occurs after dosing.

If the AE severity on the second record is worse than the severity on the first record, then only count the second AE as treatment-emergent. But, if the severity improves (second record severity is less severe than the first record severity), then neither record is counted as treatment-emergent.

Case 2: Both AE records in the pair occur after first dosing.

If the AE severity on the second record is worse than the severity on the first record, then count both records as treatment-emergent. But, if the severity improves, then only count the first record as treatment-emergent.

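### The Possible rating in Protocol 9.4.3.1 requires other causes to be excluded, which conflicts with 9.3.2 and 9.2 and biases the related adverse event tables downward for events that resemble SMA

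*Protocol*

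**What the plan says.** Protocol 9.4.3.1 gives the investigator four causality ratings:

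- **Related:** "There is clear evidence that the event is related to the use of Study Drug". A positive re-challenge is named, but only as an example.
- **Possible:** "The event cannot be explained by the subject's medical condition, concomitant therapy, or other causes". A plausible time relation to dosing is also required.
- **Unlikely/Remote:** "An event for which an alternative explanation is more likely", or the timing makes a causal link unlikely.
- **Not Related:** "The event can be readily explained by the subject's underlying medical condition", by concomitant therapy or by another cause, and the investigator therefore believes that there is no relationship.

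The same section adds: "For reporting purposes, Unlikely/Remote will be grouped together with Not Related". Under Protocol 9.4.3 the rating is the investigator's opinion and is recorded on the adverse event form.

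Protocol 9.3.2 sets a different standard: "A suspected adverse reaction is any adverse event for which there is a reasonable possibility that the drug caused the adverse event". Protocol 9.2 applies that same standard when the sponsor decides whether an event is a suspected unexpected serious adverse reaction.

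SAP 3.6.1 builds its tables from the investigator's rating: "Related adverse event is defined as those events with related or possible related relationship to study drug". This definition governs the related table, the related-by-severity table and the serious-and-related table.

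Protocol 3.7 requires a dose limiting toxicity (DLT) to be possibly or definitely related to the drug, glossed as substantially less likely to occur without it, "and that is not a known: 1) sign or symptom of SMA disease" or a known effect of the lumbar puncture.

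**The concern.** Protocol 2.1 says that children with Type I SMA usually die of respiratory failure by the age of 2 years. The disease is therefore a ready candidate explanation for respiratory and motor events in these infants. Under the wording of Possible, a candidate explanation is enough to bar the rating, even when the drug is about as plausible a cause.

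The harm affected is aggravation of the disease by the drug or the procedure. All subjects receive the drug, so no concurrent group shows how often such events would occur without it. Attribution is one of the few planned ways to separate drug from disease, and safety and tolerability are a secondary objective. If the rating screens out events because they look like SMA, a short related table says little about them.

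**Working it through.** The documents state no expected number of related events, so there is no figure to reproduce. The check has two parts: the wording, and how far the wording can move the tables.

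**1. Wording.** Take an event with plausible timing that SMA could explain and the drug could equally well have caused.

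| Standard | What it needs | Does the event meet it? |
|---|---|---|
| Related (9.4.3.1) | Clear evidence of drug cause | No, the evidence is balanced |
| Possible (9.4.3.1) | No explanation by disease, therapy or other cause, and plausible timing | No, SMA could explain it |
| Unlikely/Remote (9.4.3.1) | An alternative that is more likely, or timing against the drug | Not clearly, the alternatives are even and the timing fits |
| Not Related (9.4.3.1) | Readily explained otherwise, and investigator believes no relationship | Not clearly, a drug cause is not ruled out |
| Suspected adverse reaction (9.3.2, 9.2) | Reasonable possibility of drug cause | Yes |

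The event is a suspected adverse reaction under 9.3.2 but fits no rating cleanly. If the investigator keeps to the wording, neither of the two ratings that SAP 3.6.1 counts is available. The two ratings left are pooled and stay out of the related tables. Relative to the standard in 9.3.2, the bias for such events is therefore downward.

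**2. Size.** The documents supply only the planned 8 to 20 subjects (Protocol 3.3). Two quantities have to be assumed:

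- *d*: the proportion of infants with a drug-caused adverse event.
- *s*: the share of those infants whose drug-caused event resembles SMA.

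As a worst case, every SMA-like event misses the related table and every other drug-caused event enters it. Background events rated Possible are left out. Then:

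- Expected infants in the related table = *n* × *d* × (1 − *s*)
- Chance of at least one = 1 − [1 − *d*(1 − *s*)]^*n*

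Example: *n* = 20, *d* = 30%, *s* = 50% gives 20 × 0.30 × 0.50 = 3.0 infants, and 1 − 0.85^20 = 96%.

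Each cell shows expected infants, with the chance of at least one in brackets:

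| *n*, *d* | *s* = 0 | *s* = 50% | *s* = 75% | *s* = 90% | *s* = 100% |
|---|---|---|---|---|---|
| 20, 30% | 6.0 (99.9%) | 3.0 (96%) | 1.5 (79%) | 0.6 (46%) | 0 (0%) |
| 20, 10% | 2.0 (88%) | 1.0 (64%) | 0.5 (40%) | 0.2 (18%) | 0 (0%) |
| 8, 30% | 2.4 (94%) | 1.2 (73%) | 0.6 (46%) | 0.24 (22%) | 0 (0%) |

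The table shrinks by the factor (1 − *s*). It comes close to empty only if nearly all drug-caused events resemble SMA, or if drug-caused events are rare or the sample is small.

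**The case against.** The strongest reply is that the events are not lost. SAP 3.6.1 tabulates all treatment-emergent events, all of them by severity, and all serious ones, without regard to the rating. SAP 3.6.1.1 shows events by 90-day interval. SAP 3.6.1.2 shows them by dosing period and within 24 and 72 hours of a dose. SAP 3.4.1 gives subject-year rates for serious respiratory events, respiratory infections and related hospitalizations. Event-free survival and CHOP INTEND measure ventilatory and motor decline directly. The Data and Safety Monitoring Board (DSMB) reviews safety throughout, and the sponsor makes its own reasonable-possibility assessment under Protocol 9.2.

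All of this stands, and it limits the consequence. It does not repair the related tables. None of these displays has a planned comparator, so they show the events without separating drug from disease. The missing comparator comes from the single-arm design, and no causality wording would supply one. The 72-hour windows cover 12 doses × 3 days = 36 of 1,352 days, or 2.7%, while Protocol 2.4 estimates a half-life of 4 to 6 months in spinal tissue and CSF.

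A second reply is that the rating is an opinion and that Related stays open on clear evidence. This also stands. A reader might infer that every SMA-like event must be filed as not related, but the text does not say so. The balanced case falls into a gap, and investigators may resolve it differently.

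**Conclusion.** The concern holds as a conflict between definitions with a bias of known direction and unknown size. Possible in 9.4.3.1 is narrower than the standard in 9.3.2 and 9.2. A balanced event has no clean category, and the related tables under-count SMA-like respiratory and neuromuscular events. The direction assumes that investigators apply the wording as written. The (1 − *s*) factor is a worst case, and *d* and *s* are assumptions.

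Two stronger readings are not supported:

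- A reader might infer that the related tables will be near zero whatever the drug does. Laboratory, CSF or ECG findings that SMA and other causes cannot explain can still be rated Possible. Even in the worst case above, 20 infants with 30% incidence and half the events SMA-like give a 96% chance of at least one infant in the table.
- A reader might try to count the hidden events. If the drug doubled an assumed background of 1 to 3 respiratory events per subject-year, 20 infants followed for 3.7 years would have 20 × 3.7 × 1 = 74 to 20 × 3.7 × 3 = 222 excess events. With 8 infants the range is 30 to 89. The documents give no background rate, and full follow-up of every infant cannot be assumed in this disease, so these figures do not measure the bias.

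The plan should be changed, but the defect does not hide the events themselves.

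**What to change.** 1. **SAP 3.6.1.** Add a supportive display of treatment-emergent adverse events and serious adverse events by each of the four ratings: Related, Possible, Unlikely/Remote and Not Related. Cover at least the respiratory, infection and neuromuscular terms. The existing related tables and their grouping can stay, so no event judged to have a likelier alternative cause is relabelled as related. State next to the display that, for these terms, a low related count is not evidence against aggravation of SMA by the drug.
2. **Protocol 9.4.3.1.** Reconcile the wording of Possible with the reasonable-possibility standard in 9.3.2 and 9.2, so that a possible disease cause does not by itself rule out the rating. Flag events rated before and after the change, because one table would otherwise mix two standards.
3. **Protocol 3.7.** The DLT definition relies on possible relatedness, adds a gloss of its own and excludes known signs of SMA. It must be reconciled with 9.3.2, 9.2 and 9.4.3.1. A DLT leads to discontinuation of treatment under 8.8, so the sponsor and the DSMB need to settle this. No DLT rule is proposed here.

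**Cost.** The first item is one extra set of tables from ratings already collected. The second is a mid-study wording change, after which more events will appear as possibly related.
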